## 2 STUDY OBJECTIVES

### 2.1 Primary

- To assess the safety of a single intravenous (IV) dose of ATYR1923.

### 2.2 Secondary

- To assess the preliminary effects of ATYR1923 on clinical outcome measures of SARS-CoV-2 infection.

### 2.3 Exploratory

The exploratory objectives are:

- To explore the preliminary efficacy of ATYR1923 for SARS-CoV-2 infection.
- To assess the PD of a single IV dose of ATYR1923.
- To assess the impact of a single IV dose of ATYR1923 by measuring potential biomarkers of COVID-19 disease.

## 3 INVESTIGATIONAL PLAN

### 3.1 Overall Study Design and Plan

Study ATYR1923-C-003 is a randomized, double-blind, placebo-controlled study to evaluate the safety, PD, and efficacy of ATYR1923 in hospitalized subjects with SARS-CoV-2 related severe pneumonia not requiring mechanical ventilation.

Eligible patients will be randomized 1:1:1 to a single IV dose of ATYR1923 1 mg/kg, ATYR1923 3 mg/kg, or placebo. Study drug (ATYR1923 or placebo) will be added onto institutional standard of care (ISOC) for treating SARS-CoV2 infection.

A single dose of study drug will be administered on Day 1. All study drug will be administered in the hospital setting; patients who are intubated after randomization but prior to study drug administration are no longer eligible to receive study drug. As this is a single-dose study, the treatment period is 1 day. Thereafter, all patients will be followed for 60 days post-treatment. The schedule of study assessments over this period is dependent on the duration of hospitalization and whether or not the patient requires intubation.

### 3.1.1 Hospitalized, Non-intubated Patients

**While hospitalized**, non-intubated patients will have study assessments performed on Days 2, 3, 4, 5, 6, 7, 10, and 14 and/or Discharge.

If the non-intubated patient is discharged prior to Day 14, the assessments scheduled for Day 14 and/or discharge will be completed at the time of discharge. If discharge occurs on another scheduled study assessment day (ie, any day between Days 2 and 10), the Day 14 and/or discharge assessments supersede that study assessment day and the patient then will proceed to outpatient telephone contact (TC) follow-up visits. If a patient is discharged prior to Day 14, then outpatient TC follow-up visits are to be conducted on Day 7 (as applicable) and Day 14.

If the non-intubated patient is discharged on Days 15-20, the patient is to have the assessments scheduled for Day 14 and/or discharge performed on the day of discharge. If the patient is hospitalized for  $\geq 21$  days, the Day 14 assessments are to be performed weekly (Days 21, 28, 35, etc.) until discharge (with the exception of pharmacokinetics [PK], which is to be done only at Day 28). After discharge, the patient will proceed to the next scheduled outpatient TC follow-up visit. (Thus, if a patient remains hospitalized on Day 28, the Day 28 TC follow-up visit need not be conducted.)

### 3.1.2 Hospitalized, Intubated Patients

In the event that a patient requires intubation **while hospitalized**, ISOC assessments and interventions will supersede study assessments for the duration of intubation, with the exception of the World Health Organization (WHO) Scale and sample collection for anti-drug antibody (ADA) and Jo-1 antibody (Ab), which will continue to be collected as per the Schedule of Assessments ([Appendix 6.1](#)) on Days 5, 7, 10, 14 and weekly thereafter. The following clinical assessments will be collected and analyzed as available per the institution's electronic medical records.

- Date and time of intubation and extubation.
- Adverse events (AEs) (including new infections). In the case of new infections, the site and source of culture are to be recorded.
- Concomitant medications.

Patients will resume the study assessment schedule upon extubation. (Thus, for example, if an intubated patient is extubated on Day 7, they will resume the study assessment schedule on Day 7).

Extubated patients will have the assessments scheduled for Day 14 and/or discharge performed at the time of hospital discharge and will attend Days 28 and 60 TC follow-up visits.

If the patient is hospitalized for  $\geq 21$  days, assessments are to be performed weekly (Days 21, 28, 35, etc.) until discharge (with the exception of PK, which is to be done only at Day 28). After discharge, the patient will proceed to the next scheduled outpatient TC follow-up visit. (Thus, if a patient remains hospitalized on Day 28, the Day 28 TC follow-up visit need not be conducted.)

### 3.1.3 Independent Data Safety Monitoring Board

An independent Data Safety Monitoring Board (DSMB) will review the progress of the study and perform interim reviews of safety data at regular intervals beginning after the sixth patient has been dosed, and at a frequency guided by the enrollment rate and DSMB recommendation. Details will be documented within the DSMB Charter.

### 3.1.4 Determination of Sample Size

For this study, no prospective calculations of statistical power have been made. The sample size has been selected to provide information on safety, tolerability, PK, and efficacy following single doses of ATYR1923. There will be 30 patients randomized 1:1:1 to ATYR1923 1 mg/kg, 3 mg/kg, or placebo, respectively.

### 3.1.5 Planned Interim Analysis

A soft-lock of the data base is planned for an ad hoc safety Interim Analysis (IA). The IA will be reviewed by an designated sponsor team unblinded to treatment group to determine the continuation of the trial. Timing of the IA rests with the sponsor. A separate IA SAP and separate IA TFL Shells will be developed.

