4. INVESTIGATIONAL PLAN

4.1. Overall Study Design and Plan

Study ATYR1923-C-003 is a randomized, double-blind, placebo-controlled study to evaluate the safety, PD and efficacy of ATYR1923 in subjects with SARS-CoV-2 related severe pneumonia. SARS-CoV-2 infection will be confirmed using a polymerase chain reaction (PCR) based test during Screening. The Investigator, Sponsor, and patient will be blinded to treatment assignment; study center pharmacy personnel will be unblinded.

Eligible patients will be randomized 1:1:1 to a single IV dose of ATYR1923 1 mg/kg, ATYR1923 3 mg/kg, or placebo. Study drug (ATYR1923 or placebo) will be added onto institutional standard of care (SOC) for treating SARS-CoV2 infection.

A single dose of study drug will be administered on Day 1. All study drug will be administered in the hospital setting; patients who are intubated after randomization but prior to study drug administration are no longer eligible to receive study drug. As this is a single-dose study, the treatment period is 1 day. Thereafter, all patients will be followed for 60 days post-treatment. The schedule of study assessments over this period is dependent on the duration of hospitalization and whether or not the patient requires intubation.

- ***While hospitalized***, non-intubated patients will have study assessments performed on Days 2, 3, 4, 5, 6, 7, 10, and Day 14 and/or Discharge.
 - If the non-intubated patient is discharged prior to Day 14, the assessments scheduled for Day 14 and/or Discharge will be completed at the time of discharge. If discharge occurs on another scheduled study assessment day (ie, any day between Day 2 and 10), the Day 14 and/or Discharge assessments supersede that study assessment day and the patient then will proceed to outpatient telephone contact (TC) follow-up visits.
 - If a patient is discharged prior to Day 14, then outpatient TC follow-up visits are to be conducted on Day 7 (as applicable) and Day 14.

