6.8. Data Safety Monitoring Board

Ongoing review of safety and tolerability data will be performed by the Medical Monitor and aTyr Pharma personnel. (The Investigator, Sponsor, and patient will be blinded to treatment assignment).

An independent DSMB will review the progress of the study and perform interim reviews of safety data at regular intervals beginning after the 6th patient has been dosed, and at a frequency guided by the enrollment rate and DSMB recommendation.

The Food and Drug Administration will be notified if any patient is withdrawn for safety reasons and of any decision to pause enrollment or terminate the study.

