## REVISION HISTORY

Version No.	Effective Date	Summary of Change(s)
1.0	09 Dec 2020	New document
2.0	05 Mar 2021	
Correction of typographic errors
 
Post-unblinding Modifications after sponsor review:
 
 
• New definition and analysis of Time to recovery with WHO scale score <math>\leq 3</math> without supplemental oxygen added, see Section 4.9.4.1
 
• additional baseline categories, see Section 4.7
 
• additional concomitant medication of special interest, see Section 4.8
 
• Grading added for Urinalysis, see Section 6.3
 
• Efficacy Evaluation Analysis Set added, see Section 4.5
 

3.0	24 Mar 2021	
Minor Post-unblinding Modifications after sponsor review:
 
 
• Update Time to recovery with WHO scale score <math>\leq 3</math> without supplemental oxygen
 

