#### 4.5 Analysis Sets

**All Screened** consists of all subjects who provide written informed consent.

**Randomized Set** comprises all patients randomized regardless of whether they received study treatment. Patients will be summarized and analyzed ‘as randomized,’ ie, by randomized treatment group.

**Modified Intention-to-Treat Set (mITT Set)** comprises all patients randomized who have received any amount of study drug. Patients will be summarized and analyzed ‘as randomized,’ ie, by randomized treatment group.

**Safety Set** is defined as all randomized patients who received any amount of study drug. Patients will be summarized and analyzed ‘as treated,’ ie, by actual treatment group.

**Pharmacokinetic Set (PK Set)** is defined as patients that receive at least one dose of study drug and have at least 1 evaluable post-dose PK sample.

A by-patient listing of analysis set details including patient identifier, inclusion/exclusion flag for each set, and reason for exclusion from each set.

**Efficacy Evaluation Set (EE Set)** comprises all patients randomized and dosed who do not have any major violations or other findings upon medical review that the Sponsor determines might impact the efficacy evaluation.

**Technical Note:** The sponsor will provide a CSV file containing a list of all subjects and a flag if that subject will be included or exclude from EE Set.

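### SAP 3.1.5 gives an unblinded sponsor team the decision on continuing the trial, although the protocol states that the Sponsor is blinded and assigns interim safety review to an independent DSMB

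*SAP*

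**What the plan says.** Protocol 4.1 sets the blind: "The Investigator, Sponsor, and patient will be blinded to treatment assignment; study center pharmacy personnel will be unblinded". Protocol 6.8 repeats it ("The Investigator, Sponsor, and patient will be blinded to treatment assignment") beside the description of the sponsor's own ongoing safety review. The same section gives interim safety review to an independent DSMB, starting after the sixth patient is dosed. SAP 3.1.3 keeps that DSMB role and leaves the details to a charter. Under protocol 7.1.3.1, a SUSAR leads to an unblinded review by the DSMB, which then gives the sponsor a recommendation.

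SAP 3.1.5 plans something different. After a soft lock, an interim analysis labelled as safety is to be reviewed by a "designated sponsor team unblinded to treatment group to determine the continuation of the trial". On when this happens, the SAP says only: "Timing of the IA rests with the sponsor". On everything else it says: "A separate IA SAP and separate IA TFL Shells will be developed".

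**The concern.** The protocol presents a trial in which the sponsor does not know treatment assignment and a body outside the sponsor looks at accumulating safety data. The SAP puts people inside the sponsor in possession of arm-level results during the trial and gives them the continuation decision. Anyone who reads only the protocol would not know this.

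It matters because the sponsor is not a passive recipient of the data:

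- Under protocol 9.1.3, an event is serious if either the investigator or the sponsor considers it so. Serious TEAEs are part of the primary endpoint (SAP 3.4.1).
- Under SAP 4.5, the sponsor judges which findings exclude a patient from the Efficacy Evaluation Set, and delivers the result directly: "The sponsor will provide a CSV file containing a list of all subjects and a flag". That set is used for time to discharge, recovery and improvement, alongside the mITT Set.

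If the people who have seen results by arm also take part in these judgments, the judgments are no longer blinded. Nothing in the text rules that out.

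**Working it through.** No arithmetic applies. The documents give no power calculation (protocol 10.1.3, SAP 3.1.4), make no multiplicity adjustment (SAP 4.9.2), and state no interim alpha and no stopping boundary. An effect on error rates therefore cannot be derived. The check is a comparison of texts.

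1. **Is the sponsor blind stated without exception?** Protocol 4.1 names site pharmacy personnel as unblinded. Protocol 6.1 and 7.1.5 add a designated unblinded study team member for dispensing, the person who produces the schedule, the PK laboratory, and emergency code-breaking by the investigator. Protocol 7.1.3.1 adds the DSMB after a SUSAR. The protocol does list its exceptions, and a sponsor team that reviews results by arm is not among them.

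2. **Does any protocol text permit SAP 3.1.5?** Three places come close.
   - Protocol 10.2.1 leaves the details of interim analyses to the SAP. That permits an interim analysis but does not lift the sponsor blind.
   - Protocol 10.1.2 foresees treatment codes being unblinded after an interim analysis, but does not say to whom.
   - Protocol 6.6 lets the sponsor end the study after consulting the investigator, but does not mention unblinded data.

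3. **Is the departure declared?** SAP Table 1 lists changes from protocol version 5.0. Its only entry redefines the time-to-improvement endpoint. The unblinded sponsor review is not there.

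4. **Is the team separated from trial conduct?** The SAP calls it designated. It gives no roles, no barrier to operational or analysis staff, no continuation criteria and no data scope.

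5. **How does the team relate to the DSMB?** SAP 3.1.3 and 3.1.5 stand close together, and neither refers to the other. If the DSMB and the sponsor team disagreed, the documents do not say which would prevail.

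6. **Is the look confined to safety?** It is labelled so. Yet SAP 4.9.1, within the efficacy section, reports no differences from the interim analysis. This leaves open whether efficacy tables were included and does not settle it either way.

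7. **Has it already happened?** SAP 3.1.5 is in the future tense. The current SAP is version 3.0 of 24 March 2021, and its revision history describes version 2.0 of 5 March 2021 under "Post-unblinding Modifications after sponsor review". Treatment codes had therefore been opened to someone by then. Whether this was at the interim or the final unblinding is not stated.

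**The case against.** The strongest reply is that the protocol anticipates an interim unblinding and hands its details to the SAP, that a designated team suggests a small closed group, and that the interim SAP and the DSMB Charter, which are not among the documents, may hold every safeguard asked for here. This stands in part. The absence of a described separation is not proof that there was none, and an interim analysis as such breaks no rule. It does not answer the contradiction: the protocol twice calls the Sponsor blinded, and the SAP's list of changes is silent.

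Several limits on the damage also stand. SAP 3.1.5 unblinds neither investigators nor patients, and investigators rate intensity and causality of adverse events. Membership of the mITT and Safety Sets follows mechanically from randomization and dosing. SAP 4.6.2 requires set assignment to be agreed at a blinded review before lock and final unblinding, although the revision history lists the Efficacy Evaluation Set among the changes made after unblinding. P-values are declared exploratory.

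A reader might infer three stronger things, which the documents do not support:

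- That the interim team drove the post-unblinding SAP changes or the Efficacy Evaluation Set. Nothing ties them together, and the changes may have followed the final unblinding.
- That the comparisons carry a bias no analysis can remove. With sites blinded and the main analysis sets mechanical, this is not shown.
- That the small arms give the problem a size, since one reclassified patient moves an arm's proportion noticeably. That is a property of the sample size, not a measured effect of the interim look.

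Nor does the SAP say that the sponsor team performs the analysis; it says the team reviews it.

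**Conclusion.** The point holds as an unreconciled contradiction with a practical consequence. Read together, the two documents claim a sponsor blind that the plan does not deliver, and they do not prevent unblinded sponsor staff from taking part in judgments of seriousness or in Efficacy Evaluation Set membership. It should be corrected. It does not by itself invalidate the trial.

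The size cannot be stated as a number. The exposure lies in sponsor judgments made after the interim look, not in a type I error rate. The conclusion assumes that the unseen interim SAP and DSMB Charter do not already name the team, separate it and define its relation to the DSMB. If they do, the remaining defect is that the protocol and SAP Table 1 do not disclose the arrangement.

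**What to change.** **If the interim analysis has not been done**, take one of two routes.

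- Route the unblinded tables through the existing DSMB, supported by an unblinded independent statistician, at a trigger stated in advance (for example a fixed number of patients dosed). Only a recommendation goes to the sponsor.
- If a sponsor team must be unblinded, amend protocol 4.1 and 6.8 to say so, name the roles, and state how their decision relates to the DSMB's. Bar them from decisions on AE seriousness, protocol deviations, analysis sets and the SAP.

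**If it has been done**, rewording SAP 3.1.5 cannot restore the blind. List the departure in SAP Table 1 and in the CSR. State who was unblinded, when, and to which data, including whether efficacy was shown. Label as unblinded any analysis-set or endpoint decision in which those people took part.

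**Cost.** Before the look, the DSMB route needs SAP and charter wording and an unblinded independent statistician; the DSMB already exists. The other route needs a protocol amendment. The downside is that the sponsor sees arm-level data later or through fewer people. After the look, the cost is disclosure text and some reconstruction of who took part in which decision.

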## 3.2 Changes in the Conduct of Planned Analyses

Changes not mentioned in the CSP or SAP will be clearly indicated in the Clinical Study Report. Any post hoc analyses after database lock will clearly be labelled as post hoc.

**Table 1 Changes in the Conduct of Planned Analyses**

CSP V5.0	Changes
Secondary Endpoint: “Time to improvement from inpatient hospital admission based on at least a 1 point reduction in WHO Ordinal Scale score.”	Patients are hospitalized prior study start and therefore first WHO Scale score to be collected during Screening. Secondary Endpoint definition to be changed to:

CSP V5.0	Changes
	“Time to improvement from baseline on at least a 1 point reduction in WHO Ordinal Scale score.”

### 3.3 Final Database Lock

The study database will be finally locked when all patients completed the study. The study will be considered complete when the last patient completes the Day 60 TC follow-up visit and any necessary follow-up for Jo-1 Ab positivity or ongoing study drug-related treatment-emergent AEs (TEAEs) has been completed and cleaned.

### 3.4 Endpoints

#### 3.4.1 Primary

- Incidence of TEAEs, including serious and severe TEAEs, overall and by severity.

#### 3.4.2 Secondary

- Time to hospital discharge,
- Time to recovery (WHO score  $\leq 3$ ),
- Proportion of patients achieving recovery by Day 14 and Day 28,
- Duration of supplemental oxygen ( $O_2$ ) requirement,
- Number of days with fever (temperature  $>100.4^{\circ}\text{F}$  [ $38.0^{\circ}\text{C}$ ]),
- Change from baseline in WHO Ordinal Scale score on Days 5, 7, 14, 28, and 60,
- Time to improvement from baseline based on at least a 1 point reduction in WHO Ordinal Scale score,
- All-cause mortality at Days 14, 28, and 60.

#### 3.4.3 Exploratory

- Change from baseline in supplemental oxygen requirement at Days 3, 5, 10, 14, and discharge.
- Proportion of patients requiring intubation, and among those patients, number of days in intubation.

- Change from baseline in inflammatory biomarkers and cytokines including: C-reactive protein (CRP), interferon gamma (INF  $\gamma$ ), interleukin (IL)-6, IL-2, IL-7, IL-10, tumor necrosis factor-alpha (TNF $\alpha$ ), macrophage inflammatory protein-1 (MIP1), C-X-C motif chemokine 10 (CXC-10), and monocyte chemoattractant protein-1 (MCP-1).
- Change from baseline in potential markers of COVID-19, including serum ferritin and D-dimer.

## 4 STATISTICAL METHODS

### 4.1 Data Quality Assurance

All tables, figures and data listings to be included in the report will be independently checked for consistency, integrity, and in accordance with PAREXEL standard procedures.

### 4.2 General Presentation Considerations

**Baseline:** the last available pre-treatment assessment, unless otherwise specify. All assessments should have time collected. If time is not collected and date of assessment is the same as study drug administration date then assessment will be assumed to be collected prior to treatment unless schedule of assessments and protocol indicate planned collection is always after dosing.

For baseline of oxygen use, total oxygen use in 24 hours before drug administration date.

**Day-of-Discharge (DoD):** day when patient is discharged from the hospital.

**Date of discharge:** date patient is discharged from the hospital.

**Early Termination (ET):** day when patient withdraws from the study before completion.

**End-of-Study (EOS):** the EOS assessment is at Day 60 for patients who complete the study.

**End of study date:** date of EOS assessment (Day 60) if patient completes the study or date of early withdrawal if patient discontinues early, or date of death.

**Study Day:** <Assessment Date> - study drug administration date + 1 if <Assessment Date> is on or after study drug administration date. <Assessment Date> - study drug administration date, if <Assessment Date> is before study drug administration date.

Durations are generally calculated as the stop date - start date +1, if not otherwise stated.

For elapsed time (eg, time since the initial diagnosis) is calculated as reference date - event date.

If more than one laboratory value is available for a given study day, the last valid observation will be used in summaries, unless otherwise stated. If it is not possible to determine which is the last measurement due to missing times, then the average of all measurements for that study day will be used as the value for that study day. All observations will be presented in listings.

Laboratory data will be presented in standard units.

Continuous data will be summarized in terms of the mean, standard deviation (SD), median, minimum, maximum and number of observations, unless otherwise stated. Continuous data that are expected to be skewed will be presented in terms of the maximum, upper quartile, median, lower quartile, minimum and number of observations. The minimum and maximum will be reported to the same number of decimal places as the raw data recorded in the database. The mean, median, lower quartile and upper quartile will be reported to one more decimal place than the raw data recorded in the database. The SD will be reported to two more decimal places than the raw data recorded in the database. In general, the maximum number of decimal places reported shall be four for any summary statistic.

Categorical data will be summarized in terms of the number of patients providing data at the relevant time point (n), frequency counts and percentages. Any planned collapsing of categories will be detailed in the SAP text and the data displays.

Percentages will be presented to one decimal place. Percentages will not be presented for zero counts. Percentages will be calculated using N as the denominator, unless otherwise stated. If sample sizes are small, the data displays will show the percentages, but any textual report will describe frequencies only. Changes from baseline in categorical data will be summarized using shift tables where appropriate.

P-values greater than or equal to 0.001, in general, will be presented to three decimal places. P-values less than 0.001 will be presented as “<0.001”. Confidence intervals (CIs) will be presented to one more decimal place than the raw data.

